### 5.12.3 Secondary Efficacy Endpoints

The secondary efficacy endpoints also include the following rates.

- Disease Control Rate
- Complete Response Rate
- Overall Response Rate in tumors a Combined Positive Score  $\geq 20$  and  $\geq 50$

The secondary efficacy endpoints include the following time-to-event parameters by RECIST v1.1.

- Duration of Response
- Duration of Response in Tumors with a Combined Positive Score  $\geq 20$  and  $\geq 50$
- Progression-Free Survival
- Overall Survival

Analysis for all rates will be the same as performed for the primary endpoint. Time-to-event parameters will be compared descriptively, using quartiles and corresponding confidence intervals. Comparison between treatment arms for progression-free survival and overall survival will be summarized using a stratified log-rank test.

### 5.12.4 Secondary Efficacy Analysis

The interim analysis for PFS and OS will be conducted once all patients are treated and followed for a minimum of 3 months (2 radiologic scans). The final analysis for PFS and OS will be conducted after all patients have been followed for a minimum of 15 months, unless the study is deemed futile at the interim or primary ORR analysis stage.

#### 5.12.4.1 Disease Control Rate and Complete Response Rate

Disease control rate (DCR) is defined as the proportion of patients with a best overall response of CR, PR, or SD. Confirmation by repeat assessments is required for a BOR of CR or PR.

Complete response rate (CRR) is defined as the proportion of patients with a best overall response of CR. Confirmation by repeat assessments is required.

The statistical analysis of DCR and CRR will be the same as performed for ORR described in [Section 5.12.2](#).

#### 5.12.4.2 Duration of Response

Duration of response (DOR) is defined as the date of the patient's first BOR of CR or PR to the earliest date of documented progression or to death if no prior evidence of disease progression. DOR will be calculated as follows for all patients in the FAS population with a confirmed objective response. The date of the first confirmed response is based on the first instance of CR or PR that is confirmed by repeat assessments at least 4 weeks later.

QMD Ref: Worldwide-TMP-ST-054-1.0_Effective: 12Aug2022	Governing QMD: Worldwide-SOP-ST-026
Confidentiality Statement	
This document is the property of Worldwide Clinical Trials Inc. and may not be duplicated, copied, altered or removed from company without prior approval from Worldwide Quality Assurance or in compliance with Worldwide Standard Operating Procedures.	

Worldwide Clinical Trials Controlled Quality Management Document			
 WORLDWIDE CLINICAL TRIALS	Sponsor:	Flamingo Therapeutics	
	Protocol Number:	FLM-6774-201	
STATISTICAL ANALYSIS PLAN			

$$DOR \text{ (Months)} = \frac{(Date \text{ of } PD, \text{Death, or censoring} - Date \text{ of } 1^{\text{st}} \text{ confirmed CR or PR}) + 1}{30.4375}$$

DOR may be censored to a stop date other than PD or death, as described in the censoring rule table of [Section 5.12.4.5](#).

Kaplan-Meier estimates of 25th, 50th and 75th percentiles for DOR will be presented. Corresponding 95% confidence intervals using Greenwood's formula will be provided. Minimum and Maximum DOR will be presented.

The following SAS code will be used.

```
proc lifetest data=adtte timelist=3 6 9 12 reduceout outsurv=<outdata>;
  time aval*cnsr(1);
  by trt01pn;
run;
```

#### 5.12.4.3 Progression Free Survival

PFS is defined as the time from date of randomization to first progression of disease (PD) or death due to any cause, whichever occurred first, where the disease progression will be determined based on RECIST v1.1 criteria. The analysis of this endpoint will be based on FAS population.

$$PFS \text{ (Months)} = \frac{(Date \text{ of } PD \text{ or Death or Censoring} - Date \text{ of randomization}) + 1}{30.4375}$$

PFS may be censored to a stop date other than PD or death, as described in the censoring rule table of [Section 5.12.4.5](#).

PFS median follow-up time (MFT) is defined as the time from date of randomization until the time where a subject is censored based on censoring rules for PFS. In the calculation for PFS MFT, documented PD or death will be considered censored events, rather than events.

Kaplan-Meier estimates of 25th, 50th and 75th percentiles for PFS and PFS MFT will be presented. Corresponding 95% confidence intervals using Greenwood's formula will be provided. Minimum and Maximum PFS will be presented.

A Stratified Log-Rank test will be conducted, stratified for Baseline CPS category, to compare both treatment arm and the p-value will be provided. The following SAS code will be used:

```
ods output homtests=<outdata>;
proc lifetest data=adtte;
  time aval*cnsr(1);
  strata cpsgr1 / group=trt01pn;
run;
```

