3.4 Randomization and Blinding

Randomization will be managed centrally through an Interactive Response Technology (IRT) system. Patients will be randomized in a 2:1 ratio to either danvatirsen + pembrolizumab or pembrolizumab monotherapy. Randomization will be stratified by Eastern Cooperative Oncology Group (ECOG) performance status (0 vs. 1 [Appendix 1]) for patients enrolled under the original protocol or Amendment 1.

For patients enrolled following this amendment, randomization will be stratified by the CPS (CPS ≥ 1 and < 20 vs. CPS ≥ 20) obtained during screening, instead of ECOG performance status. Considering the addition of the new subgroup of subjects (CPS ≥ 1 and < 20) as of this amendment, the change in stratification variables will not impact the intended randomization balance. Removing ECOG performance status as a potential second stratification variable in addition to CPS is necessary considering the limited size of the study and the 2:1 randomization ratio.

Flamingo Therapeutics

Activity and Safety of Danvatirsen and Pembrolizumab in HNSCC

8 May 2025

Trial ID: FLM-6774-201

Amendment 4

Sites will receive the randomized treatment assignment for all patients by logging into the IRT system and entering the required data.

Patients who are randomized in the IRT but do not receive study treatment will not be replaced.

Blinding is not applicable for this open-label study.

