### 4 RANDOMIZATION

Upon confirmation of eligibility, patients will be randomized in a 2:1 ratio to either Danvatirsen + pembrolizumab or Pembrolizumab monotherapy.

Study randomization will be managed centrally through an Interactive Response Technology (IRT) system. Sites will receive the randomized treatment assignment for all patients by logging into the IRT system and entering the required data.

Randomization will be stratified by Eastern Cooperative Oncology Group (ECOG) performance status (0 vs. 1) for patients enrolled under the original protocol or Amendment 1. For patients enrolled under Amendment 2 or later, randomization will be stratified by CPS ( $1 \leq \text{CPS} < 20$  vs  $\text{CPS} \geq 20$ ). The change in stratification variables will not impact the intended randomization balance.

QMD Ref: Worldwide-TMP-ST-054-1.0_Effective: 12Aug2022	Governing QMD: Worldwide-SOP-ST-026
Confidentiality Statement	
This document is the property of Worldwide Clinical Trials Inc. and may not be duplicated, copied, altered or removed from company without prior approval from Worldwide Quality Assurance or in compliance with Worldwide Standard Operating Procedures.	

Worldwide Clinical Trials Controlled Quality Management Document			
 WORLDWIDE CLINICAL TRIALS	Sponsor:	Flamingo Therapeutics	
	Protocol Number:	FLM-6774-201	
STATISTICAL ANALYSIS PLAN			

A Tumor Proportion Score (TPS) value  $\geq 30$  may be used for initial eligibility. The subject will be assigned to the  $1 \leq \text{CPS} < 20$  stratum, if  $30 \leq \text{TPS} < 50$ , or the  $\text{CPS} \geq 20$  stratum, if  $\text{TPS} \geq 50$ . However, a CPS value must be obtained and reported utilizing a tissue sample obtained prior to the start of study treatment.

Blinding is not applicable for this open-label study.

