#### Confidentiality Statement

Worldwide Clinical Trials Controlled Quality Management Document			
 WORLDWIDE CLINICAL TRIALS	Sponsor:	Flamingo Therapeutics	
	Protocol Number:	FLM-6774-201	
STATISTICAL ANALYSIS PLAN			

Probability of progression-free survival for at least 3 months, 6 months, 9 months, and 12 months along with corresponding 95% confidence intervals using the Kaplan-Meier method will be provided for the Overall column.

The hazard ratio of PFS, comparing the combination arm to Pembrolizumab, will be estimated using a Cox Proportional-Hazard model. The model will adjust for Baseline CPS category, and a corresponding 95% confidence interval will be provided. The following SAS code will be used:

```
ods output parameterestimates=<outdata>;
proc phreg data=adtte
  class trt01pn(ref='2');
  model aval*cnsr(1)=trt01pn / r1 ties=exact;
  strata cpsgr1;
  hazardratio trt01an;
run;
```

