#### 5.12.4.4 Overall Survival

Overall survival (OS) is defined as the time from randomization to death from any cause.

$$OS \text{ (Months)} = \frac{(Date \text{ of Death or Censoring} - Date \text{ of randomization}) + 1}{30.4375}$$

OS may be censored to a stop date other than PD or death, as described in the censoring rule table of [Section 5.12.4.5](#).

OS median follow-up time (MFT) is defined as the time from date of randomization until the time where a subject is censored based on censoring rules for OS. In the calculation for OS median follow-up time, documentation of death will be considered a censored event, rather than an event, and a censored OS will be considered an event.

OS and OS MFT will be analyzed the same as done for PFS. Kaplan-Meier estimates will only be calculated for the probability of survival for at least 12 month or 24 months. Hazard ratio and 95% confidence interval will be provided.

QMD Ref: Worldwide-TMP-ST-054-1.0_Effective: 12Aug2022	Governing QMD: Worldwide-SOP-ST-026
Confidentiality Statement	
This document is the property of Worldwide Clinical Trials Inc. and may not be duplicated, copied, altered or removed from company without prior approval from Worldwide Quality Assurance or in compliance with Worldwide Standard Operating Procedures.	

Worldwide Clinical Trials Controlled Quality Management Document			
 WORLDWIDE CLINICAL TRIALS	Sponsor:	Flamingo Therapeutics	
	Protocol Number:	FLM-6774-201	
STATISTICAL ANALYSIS PLAN			

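### The PFS and OS Cox models adjust only for CPS, although ECOG was the randomisation factor for the early cohort and is known for every patient

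*SAP*

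**What the plan says.** **Analysis.** SAP 5.12.4.3 specifies for PFS: "A Stratified Log-Rank test will be conducted, stratified for Baseline CPS category". Of the Cox model in the same section it says: "The model will adjust for Baseline CPS category"; the code has CPS category in the strata statement and treatment as the only covariate. For OS, SAP 5.12.4.4 says: "OS and OS MFT will be analyzed the same as done for PFS". Protocol 9.7 asks for a stratified log-rank test for PFS and OS without naming the factors.

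**Randomisation.** SAP 4 gives ECOG "performance status (0 vs. 1) for patients enrolled under the original protocol or Amendment 1" as the first stratification factor. It then changes: "For patients enrolled under Amendment 2 or later, randomization will be stratified by CPS". Protocol 3.4 explains the change: "Removing ECOG performance status as a potential second stratification variable in addition to CPS is necessary considering the limited size of the study".

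**ECOG elsewhere.** A score of 0 or 1 is an inclusion criterion (Protocol 4.1). Baseline ECOG is summarised (SAP 5.7), is a descriptive subgroup for ORR, DOR, PFS and OS (SAP 5.12.6), and appears in the forest plots (SAP 5.12.8).

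**Status of PFS and OS.** SAP 5.12.7 treats all secondary endpoints as descriptive, without multiplicity control. SAP 9 says the final analysis comes earlier than planned because the study was terminated early.

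**The concern.** Part of the trial was allocated within ECOG strata, and the model that supplies the hazard ratio does not use that factor. Protocol 3.4 introduces CPS 1 to <20 with the words "Considering the addition of the new subgroup of subjects". This suggests, though it does not state, that the ECOG-stratified cohort is entirely CPS 20 or above. If so, the CPS stratum separates none of those patients. In the later cohort ECOG was not balanced by design at all.

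The reason given for dropping ECOG concerns how many randomisation strata a small 2:1 trial can carry. It does not apply to one covariate in a Cox model, and neither document explains leaving ECOG out of the analysis.

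At stake is how the PFS and OS hazard ratios and intervals are read. No decision rule depends on them, but Protocol 1.2 expects the efficacy data to inform later studies that may be pivotal.

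**Working it through.** **1. The plan's own figures.** No power, target HR or event count is stated for PFS or OS. The only comparative power is for ORR (Protocol 9.2: 0.15 vs 0.43, 27 vs 54 patients). Exact enumeration with Beta(0.5, 0.5) priors, interim cut-off 0.96 × (39/81)^0.94 = 0.483 and final cut-off 0.96 gives power 82.6% (stated 83%, 82.7% in Table 10) and type I error 4.5% (Table 10: 4.6%). The ORR design reproduces and is not in question.

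**2. What PFS and OS can deliver.** Schoenfeld, 2:1 allocation, two-sided 5% (SAP 5.12):

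power = Φ(√(d × 2/3 × 1/3) × |ln HR| − 1.96)

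- With d = 70 and HR 0.6: √15.56 × 0.511 − 1.96 = 0.055, so power is about 52%.
- Events for 80% power at HR 0.6: (1.96 + 0.842)² / (2/9 × 0.511²) ≈ 136, more than 81 patients can supply.
- Approximate 95% CI around 0.6 with 70 events: 0.6 × exp(±1.96/√15.56) = 0.37 to 0.99.

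**3. Simulation of omitting ECOG.**

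- From the documents: 81 patients, 2:1, early cohort stratified by ECOG and later cohort by CPS, minimum follow-up 15 months.
- Assumed, because the documents are silent: 60% ECOG 1; early cohort 30% of patients, all CPS ≥20; half of later patients CPS ≥20; CPS HR 0.8; treatment HR 0.6 given ECOG and CPS; exponential times; control median 3.2 or 12 months; 18 months' accrual; ECOG HR 1.0 to 3.0.
- 2,000 trials per scenario. The Monte Carlo SE of a power figure is about √(0.5 × 0.5/2000) = 1.1 points.
- Power is for the CPS-stratified log-rank statistic (CPS only) and for the Wald test of treatment in the Cox model with ECOG added.

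| ECOG HR | Control median (mean events) | HR, CPS only | HR, CPS + ECOG | Shift | Power, CPS only | Power, CPS + ECOG |
|---|---|---|---|---|---|---|
| 1.0 | 3.2 mo (70.5) | 0.588 | 0.584 | 0.004 | 53.4% | 53.2% |
| 1.0 | 12 mo (41.8) | 0.595 | 0.591 | 0.004 | 38.1% | 36.4% |
| 1.5 | 3.2 mo (70.0) | 0.606 | 0.595 | 0.011 | 47.6% | 49.2% |
| 1.5 | 12 mo (41.8) | 0.600 | 0.591 | 0.009 | 36.2% | 35.5% |
| 2.0 | 3.2 mo (69.5) | 0.612 | 0.588 | 0.024 | 46.8% | 50.8% |
| 2.0 | 12 mo (42.0) | 0.608 | 0.589 | 0.019 | 34.2% | 36.0% |
| 3.0 | 3.2 mo (68.1) | 0.644 | 0.588 | 0.056 | 38.2% | 49.1% |
| 3.0 | 12 mo (42.4) | 0.623 | 0.587 | 0.036 | 31.7% | 36.3% |

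A separate set of runs with about 75 events gave 0.62 against 0.59 at ECOG HR 2.0, hence the range 0.02-0.03 there.

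**4. Under no treatment effect.** The CPS-only test rejected in 3.5% to 5.9% of trials across the eight scenarios. The lowest figure came with ECOG HR 3.0 and the 3.2-month median.

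**5. Chance imbalance.** In the runs with about 75 events, the proportion with ECOG 1 differed between arms by more than 10 percentage points in about 30% of trials. At ECOG HR 2.0:

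- More ECOG 1 on the combination: mean HR 0.68 with CPS only, 0.58 with ECOG added, a displacement of 0.10.
- Fewer ECOG 1 on the combination: 0.56 with CPS only, 0.60 with ECOG added, a displacement of 0.04 in the drug's favour.

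A repeat with 3,000 trials and the 3.2-month median again gave about 30% and displacements of about 0.09 and 0.04.

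**The case against.** The strongest case against runs as follows.

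- **Size is assumed.** The documents give no prognostic effect for ECOG, no ECOG 1 prevalence and no early-cohort size. At ECOG HR 1.5 the power differences are within noise, and at 2.0 they are 2 to 4 points. This stands. A reader might infer that the hazard ratio is attenuated and power is lost as matters of fact. The documents support only the conditional statement.
- **There is no planned power to lose.** PFS and OS are descriptive, 80% power at HR 0.6 is out of reach, and early termination reduces events further. This stands.
- **The average shift is a change of target.** The CPS-only model estimates an HR averaged over ECOG; the adjusted model estimates one conditional on it. A reader might infer that ignoring the early cohort's randomisation factor invalidates the test. Step 4 shows no inflation of the false-positive rate beyond what is seen with no ECOG effect.
- **The remedy does not touch the specified test.** The p-value comes from the CPS-stratified log-rank, which stays as it is. This stands, so the power columns above are no argument for changing the Cox model.
- **ECOG is not ignored.** The baseline table will show any imbalance, and PFS and OS are reported within ECOG 0 and 1. This is true, but separate estimates in small subgroups do not give an adjusted overall HR.
- **The SAP does not contradict the protocol,** which leaves the log-rank factors unnamed. Correct, and no contradiction is claimed.

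What remains is the lack of protection of the reported HR and CI against ECOG imbalance, with no reason given for the omission.

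**Conclusion.** The point holds as a modest, conditional one. The PFS and OS Cox models leave out a factor by which part of the trial was randomised and which is known for every patient. If ECOG is prognostic, the reported HR lies on average about 0.01 (ECOG HR 1.5), 0.02-0.03 (2.0) or 0.04-0.06 (3.0) closer to 1 than the ECOG-conditional HR of 0.6. These average shifts are small beside a confidence interval of roughly 0.37 to 0.99.

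Imbalance in the trial actually run is the better reason to act: in about three trials in ten the arms would differ by more than 10 points in ECOG 1, and at ECOG HR 2.0 that displaces the HR by about 0.10 one way or 0.04 the other. All these sizes rest on the assumptions in step 3. With no ECOG effect there is nothing material to correct.

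**What to change.** Before database lock, add baseline ECOG (0 vs 1) as a covariate in the PFS and OS Cox models, keeping CPS category as the stratum, and report the ECOG-adjusted HR with its 95% CI. Leave ECOG out of the model in the ECOG subgroup analyses, as SAP 5.12.6 already does for CPS in the CPS subgroup analysis of PFS. Keep the CPS-stratified log-rank as the test and do not claim that its power improves.

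Use a covariate, not CPS × ECOG strata. In the same simulations, crossing the strata changed power by −3.8 and −2.5 points (3.2- and 12-month medians) when ECOG had no effect.

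The cost is one term in the class and model statements, one extra parameter and a proportional-hazards assumption for ECOG, with no gain if ECOG is not prognostic. Under SAP 5, a change after lock would have to go into a post-lock addendum. The same code step needs editing anyway: the procedure line lacks its semicolon, and the hazard-ratio statement names trt01an while the model uses trt01pn.

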#### Confidentiality Statement

Worldwide Clinical Trials Controlled Quality Management Document			
 WORLDWIDE CLINICAL TRIALS	Sponsor:	Flamingo Therapeutics	
	Protocol Number:	FLM-6774-201	
STATISTICAL ANALYSIS PLAN			

Probability of progression-free survival for at least 3 months, 6 months, 9 months, and 12 months along with corresponding 95% confidence intervals using the Kaplan-Meier method will be provided for the Overall column.

The hazard ratio of PFS, comparing the combination arm to Pembrolizumab, will be estimated using a Cox Proportional-Hazard model. The model will adjust for Baseline CPS category, and a corresponding 95% confidence interval will be provided. The following SAS code will be used:

```
ods output parameterestimates=<outdata>;
proc phreg data=adtte
  class trt01pn(ref='2');
  model aval*cnsr(1)=trt01pn / r1 ties=exact;
  strata cpsgr1;
  hazardratio trt01an;
run;
```

#### 5.12.4.4 Overall Survival

Overall survival (OS) is defined as the time from randomization to death from any cause.

$$OS \text{ (Months)} = \frac{(Date \text{ of Death or Censoring} - Date \text{ of randomization}) + 1}{30.4375}$$

OS may be censored to a stop date other than PD or death, as described in the censoring rule table of [Section 5.12.4.5](#).

OS median follow-up time (MFT) is defined as the time from date of randomization until the time where a subject is censored based on censoring rules for OS. In the calculation for OS median follow-up time, documentation of death will be considered a censored event, rather than an event, and a censored OS will be considered an event.

OS and OS MFT will be analyzed the same as done for PFS. Kaplan-Meier estimates will only be calculated for the probability of survival for at least 12 month or 24 months. Hazard ratio and 95% confidence interval will be provided.

QMD Ref: Worldwide-TMP-ST-054-1.0_Effective: 12Aug2022	Governing QMD: Worldwide-SOP-ST-026
Confidentiality Statement	
This document is the property of Worldwide Clinical Trials Inc. and may not be duplicated, copied, altered or removed from company without prior approval from Worldwide Quality Assurance or in compliance with Worldwide Standard Operating Procedures.	

Worldwide Clinical Trials Controlled Quality Management Document			
 WORLDWIDE CLINICAL TRIALS	Sponsor:	Flamingo Therapeutics	
	Protocol Number:	FLM-6774-201	
STATISTICAL ANALYSIS PLAN			

#### 5.12.4.5 Censoring Rules for Time-to-Event Parameters

Progression-Free Survival and Duration of Response Censoring			
#	Event Description	Stop Date Used	Outcome
1	Documented radiological PD before initiation of non-study anti-cancer treatment	Date of the first tumor assessment that determined PD	Event
2	Death during the study with no prior PD and no prior initiation of non-study anti-cancer treatment	Date of death	Event
3	Radiographic PD or death after a missed (or not available / not evaluable) tumor response assessment**	Date of last adequate tumor assessment prior to missed tumor assessment	Censored
4	Patient administered new anticancer therapy prior to disease progression	Date of last valid disease assessment prior to start of new anticancer therapy	Censored
5*	No evaluable post-Baseline tumor assessment	Date of first dose	Censored
6*	Patient without documented progression or death	Date of the last valid disease assessment date	Censored
7*	Patient withdrawal or lost to follow-up	Date of the last valid disease assessment	Censored
Overall Survival Censoring			
#	Event Description	Stop Date Used	Outcome
1	Death from any cause	Date of death	Event
2	Patient withdrawal or lost to follow-up	Date of the last contact	Censored
3	Patient without documentation of death as of the data cutoff	Date of last contact where subject known to be alive.	Censored

\*Not applicable to Duration of Response

\*\*A tumor response assessment is considered missed if more than 13 weeks (91 days) has elapsed since the last image-based tumor response assessment. If a subject develops progressive disease or dies directly after this interval, the tumor response assessment will be excluded from analysis and censored to the last evaluable assessment. However, if a response assigned as CR, PR, or SD is obtained after more than 13 weeks, then the tumor response will not be excluded.

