Patients in both treatment arms will have radiologic tumor assessments every 6 weeks (± 1 week), regardless of treatment delays, until objective disease progression, initiation of new anticancer treatment, death, withdrawal of consent, or end of study, whichever occurs first.

All patients who discontinue study treatment for any reason will have a safety follow-up visit 30 days (+7 days) after the last dose of study treatment and a follow-up for AEs 90 days (+7 days) after the last dose of pembrolizumab. Patients will be followed for survival at 12-week (± 7 days) intervals until death or withdrawal of consent, whichever occurs first. Survival follow-up will continue until at least 15 months after the last patient is randomized in the study.

The study design is depicted in [Figure 1](#).

Figure 1: Study Scheme

Note: Maximum duration of pembrolizumab treatment is 24 months; there is no limit to the duration of danvatirsen treatment.

Abbreviations: PD = progressive disease; Q3W = every 3 weeks; QW = weekly; SFU = safety follow-up & survival follow-up

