6 DISCONTINUATION AND WITHDRAWAL CRITERIA

6.1 Discontinuation of Study Treatment

After consultation with the medical monitor, patients in the combination arm that are discontinued from one of the study treatments may remain in the study and continue to receive the other study treatment until a discontinuation criterion for the remaining treatment has been met.

Treatment with danvatirsen and pembrolizumab should be permanently discontinued for any of the following:

- Consent withdrawal
- Intolerable AE or an AE that meets the criteria for discontinuation
- Confirmed PD
 - Clinically stable patients who experience radiographic PD by RECIST v1.1 may continue to receive study treatment if patients are otherwise tolerating study treatment in the opinion of the Investigator and there are no signs of rapid, radiographic progression of disease or progression at critical anatomical sites (e.g., cord compression or tumor impinging on a major blood vessel) requiring urgent alternative interventions. Confirmatory imaging should be performed at least 4 weeks later for patients with PD who remain on study treatment. If PD is confirmed, the patient will withdraw from study treatment.
- Clinical progression, in absence of radiographic progression by RECIST v1.1, including intolerable signs or symptoms consistent with disease progression, rapidly worsening laboratory values or relevant tumor markers, rapid decline in ECOG performance status, or impingement of the tumor at critical anatomic sites requiring urgent interventions. Whenever possible, discontinuation due to clinical progression should be discussed with the Medical Monitor
- Pregnancy
- Significant patient non-compliance with the protocol or major protocol deviation
- Investigator decision
- Sponsor decision to end the study.

Patients who discontinue study treatment will complete end-of-treatment (EOT) procedures, safety follow-up, and will enter the survival follow-up phase, as specified in the SoA (Section 8.1). See [Section 7.6](#) for more information.

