PFS is defined as the time from randomization to the first of either disease progression or death from any cause, where disease progression will be determined based on RECIST v1.1 criteria. A patient that starts a new anticancer therapy prior to disease progression will be censored at the date of last valid disease assessment prior to the start of the new anticancer therapy. Patients without documented disease progression or death will be censored at the last valid disease assessment date. Any patient without a valid disease assessment will be censored on the day of the first dose. PFS will be summarized using Kaplan-Meier methods and compared between the 2 groups using a stratified log rank test.

Sensitivity analyses for ORR, DOR, and PFS will be repeated with the requirement of confirmation of disease progression at least 4 weeks after an initial assessment of PD. Any unconfirmed disease progression assessment will not be counted as PD in these analyses.

OS is defined as the time from randomization to death from any cause. Patients without documentation of death as of the data cutoff will be censored at the last date the patient was known alive. OS will be summarized using Kaplan-Meier methods and compared between the 2 groups using a stratified log rank test.

All efficacy analyses will be performed for two key efficacy subgroups, which includes all patients with CPS ≥ 20 and CPS ≥ 50 . Additional subgroups of interest will be defined in the SAP.

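### The SAP censors PFS and DOR when PD or death follows a scan gap of more than 91 days; Protocol 9.7 has no such rule, the SAP does not declare the change, and no planned PFS or DOR analysis keeps these events.

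*SAP*

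**What the plan says.** Protocol 9.7 makes the first of progression or death from any cause the PFS event. It censors PFS in three situations only: new anticancer therapy before progression, no event ("Patients without documented disease progression or death will be censored at the last valid disease assessment date"), and no valid assessment. For DOR it censors only for new therapy or absence of progression and death. Neither definition mentions the time since the last scan. SAP 5.12.4.3 keeps the same event, "first progression of disease (PD) or death due to any cause, whichever occurred first", and then refers to the censoring table.

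That table, in SAP 5.12.4.5, adds row 3: "Radiographic PD or death after a missed (or not available / not evaluable) tumor response assessment". The outcome is censored and the stop date is "Date of last adequate tumor assessment prior to missed tumor assessment". The footnote defines the trigger: "A tumor response assessment is considered missed if more than 13 weeks (91 days) has elapsed since the last image-based tumor response assessment". It continues: "If a subject develops progressive disease or dies directly after this interval, the tumor response assessment will be excluded from analysis". A CR, PR or SD scan obtained after the gap is kept. The mark that exempts DOR stands on rows 5 to 7 only, so row 3 applies to DOR as well as PFS.

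SAP 5.12.5 plans one sensitivity analysis, dropping response confirmation for ORR and DOR. SAP section 9 lists one change from the protocol, the early final analysis after termination of the study.

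**The concern.** Row 3 changes which events count, so the PFS and DOR that are reported will not be the endpoints the protocol defines, and nothing in the SAP tells the reader so.

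The patients affected can be foreseen. Protocol 6.1 stops treatment for "Clinical progression, in absence of radiographic progression by RECIST v1.1", and Appendix 5 says that symptomatic deterioration is not objective PD. Such a patient has no PFS event yet. If scanning lapses and the patient dies more than 91 days after the last scan, row 3 removes the death from PFS. Where the lapse is linked to deterioration, the censoring is informative.

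The table also cannot be programmed unambiguously, because one death can satisfy two rows with opposite outcomes. What is at stake is lost events in a small trial, a possible distortion of the treatment comparison, and an outcome that may depend on a programmer's choice.

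**Working it through.** **1. Protocol and SAP side by side**

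| Situation | Protocol 9.7 | SAP 5.12.4.5 |
|---|---|---|
| PD on the first scan after a gap >91 days | Event at PD | Row 3: censored at last adequate scan |
| Death without prior PD or new therapy, >91 days after last scan | Event at death | Row 2: event at death; row 3: censored at last adequate scan |
| PD after a gap, with a CR/PR/SD scan in between | Event | Event (footnote keeps the intervening scan) |

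Take a hypothetical patient whose last scan, without PD, is at week 12 (2 × 6) and who dies 14 weeks later, with no new therapy. The gap is 14 × 7 = 98 days, more than 91. Row 2 gives an event at week 12 + 14 = 26. Row 3 gives censoring at week 12. The SAP does not say which row wins.

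**2. Planned analyses that would restore these events**

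There are none for PFS or DOR. SAP 5.12.5 varies response confirmation only. The confirmed-PD sensitivity analysis in Protocol 9.7 does not restore gap events and is not carried into the SAP. The SAP table list has no alternative PFS table.

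**3. The 91-day threshold**

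Protocol 3.1 requires "radiologic tumor assessments every 6 weeks", with a window of 1 week either side.

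- Plan's figure: 13 × 7 = 91 days. This equals two intervals plus one window, (2 × 6 + 1) × 7 = 91.
- One missed scan between two in-window scans: 2 × 6 = 12 weeks, ± 1 week at each end, so 10 to 14 weeks or 70 to 98 days.
- Two missed scans: 3 × 6 = 18 weeks ± 2, so 16 to 20 weeks or 112 to 140 days.

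A PD found after a single missed scan is therefore an event at a gap of 70 to 91 days and censored at 92 to 98 days. A threshold of (2 × 6 + 2) × 7 = 98 days separates one miss from two.

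**4. Events lost (illustration on assumptions)**

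The documents give no gap rate and no PFS event count. Assume a fraction f of 81 patients stop for clinical progression with no later scan and no new therapy and are followed to death. Let the last scan fall U days earlier, U uniform on 0 to 42, and let time to death after stopping be exponential with median m.

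Share of these deaths beyond 91 days = mean over U of exp(−ln 2 × (91 − U)/m) = 0.59, 0.67 and 0.77 for m = 3, 4 and 6 months.

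- f = 15%, m = 4 months: 81 × 0.15 × 0.67 ≈ 8 events, in the 2:1 ratio about 5.4 combination and 2.7 control.
- f = 10%, m = 3 months: 81 × 0.10 × 0.59 ≈ 5.
- f = 20%, m = 6 months: 81 × 0.20 × 0.77 ≈ 12.

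For scale, Schoenfeld power is Φ(|ln HR| × √(d × 2/3 × 1/3) − 1.96). At an assumed HR of 0.6 and d = 60 events it is 46.2%. Losing 5%, 10% or 15% of events (d = 57, 54, 51) gives 44.4%, 42.4% or 40.5%.

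**5. Hazard ratio (simulation on assumptions)**

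Inputs: 27 v 54 patients, control median PFS 3.5 months, 30% of events deaths, 400 runs per case. Both rules were applied to the same data, so the paired change is what to read.

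| Gap rate, control v combination | True HR 1.0: all events → row 3 | True HR 0.7: all events → row 3 |
|---|---|---|
| 5% v 5% | 1.01 → 1.01 | 0.67 → 0.67 |
| 10% v 10% | 0.98 → 0.98 | 0.70 → 0.69 |
| 15% v 5% | 1.03 → 1.09 | 0.70 → 0.75 |
| 5% v 15% | 0.94 → 0.89 | 0.66 → 0.62 |
| 20% v 5% | 1.06 → 1.16 | 0.74 → 0.82 |

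Equal gap rates leave the hazard ratio nearly unchanged. Unequal rates move it in either direction.

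**The case against.** The strongest reply is that censoring after a long gap is a legitimate choice, that the introduction to Protocol section 9 leaves technical detail to the SAP, and that little depends on it. Much of this stands. SAP 5.12.7 makes the secondary endpoints descriptive. The affected deaths remain OS events. Protocol 7.6.3 and 7.7 require scanning to continue after stopping for reasons other than PD, and Appendix 5 asks for every effort to document progression, which should limit the gaps. The footnote does define a miss, so row 3 and its footnote are not in contradiction; the threshold problem is confined to gaps of 92 to 98 days.

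The figure of about 8 lost events is also an assumption, not an estimate. It needs full enrolment and follow-up to death, whereas the study ended early. On the same inputs about 4 of 81 events would be lost by 12 months from randomization and about 1 by 6 months.

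A reader might infer that row 3 lengthens PFS. That is not supported. The removed deaths are late by construction, and counting them at the death date tends to raise the early curve. With assumed median times to progression of 5 and 3.5 months, 15% clinical progressors and a 4-month median to death, 6-month PFS was 0.51 by the protocol rule and 0.50 by row 3 in the combination arm, and 0.39 v 0.37 in the control arm. The 15-month restricted mean was 7.41 v 7.35 and 6.03 v 5.86 months.

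What the reply does not answer is that row 3 changes the event definition without saying so, that rows 2 and 3 conflict, and that no PFS or DOR analysis follows the protocol.

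**Conclusion.** The point holds as a matter of definition, disclosure and programmability. Row 3 departs from Protocol 9.7 for both PFS and DOR, is undeclared, conflicts with row 2 for late deaths, and can treat patients with the same single missed scan differently. The consequence is lost events and possibly informative censoring.

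Its size cannot be computed from the documents. The range of about 5 to 12 of 81 rests wholly on the assumed 10% to 20% of patients and 3- to 6-month median to death, and would be smaller with short follow-up. Nor do the documents support a claim that row 3 favours one arm. The effect on DOR has not been quantified. Confirmed ORR does not use this table and is untouched. The importance is moderate: it should be corrected, but it does not threaten the primary conclusion. Which rule should be main is open to argument; that both should be run is not.

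**What to change.** - **Run PFS and DOR both ways.** Preferably make the Protocol 9.7 definition the main analysis: PD at the scan date and death at the death date whatever the gap, with the protocol's own censoring rules unchanged. Row 3 then moves to SAP 5.12.5 as a sensitivity analysis. If row 3 stays as main, declare and justify it in SAP section 9 and add the protocol-definition analysis to 5.12.5.
- **State precedence.** Say which of rows 2 and 3 governs a death without prior PD after a gap.
- **Settle the threshold.** If the rule is meant to capture two consecutive missed scans, set it at 98 days.
- **Report counts.** Give the number of patients censored by row 3 in each arm, separately for PD and death, so that an imbalance in gaps is visible.

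The cost is SAP wording, shells for the added PFS and DOR tables, and one extra run of existing code. The downside of the protocol definition is that a PD first seen after a long gap is dated late; the row 3 analysis shows how much that matters.
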